### **7.2.4 Change from Baseline to Week 24 in the FACT-An score**

The change from Baseline at Week 24 in the FACT-An scores will be analyzed using MMRM with the fixed effects of treatment, strata, visit, visit-by-treatment interaction and the FACT-An score at Baseline as covariate using an unstructured covariance matrix and the Kenward Rogers

method for calculating the degrees of freedom. Should the model fail to converge with an unstructured covariance matrix other covariance structures will be explored (unstructured will be attempted first, followed by compound symmetry, followed by AR(1) if needed). The difference between treatment groups will be estimated, along with its 95% CI and p-value.

The FACT-An total score is a key secondary endpoint. Additional FACT-An scores that will be summarized include the physical subscore, social subscore, emotional subscore, functional subscore, and anemia subscore.

Reference documents for quality of life scores may be used as needed. These include the FACT-An Scoring Guidelines, FACIT Fatigue Scale (Version 4) guidelines, and the EQ-5D-5L (Version 3.0 SEP2019) User Guide.

The ICEs and their associated strategies to handle them, will be the same as for the key secondary endpoint Change from Baseline to Week 24 in Hb level in section 7.2.2. An additional (descriptive only) summary table of change from baseline irrespective of ICEs will be created for FACT-An.

### **7.3 SECONDARY EFFICACY ENDPOINT ANALYSIS FOR PART A**

All secondary efficacy analyses will be analyzed with the ITT set.

#### **7.3.1 Number of PRBC transfusions from Week 5 to Week 24.**

The number of PRBC transfusions from Week 5 to Week 24 in each treatment group will be compared using a stratified Wilcoxon rank-sum test-p-value will be calculated. Crude rates of transfusions will be calculated for the double-blind period (Part A). Patients who withdraw from randomized treatment or receive prohibited medication before Week 24 will have the number of transfusions estimated from the duration that they were in the study until withdrawal or initiation of prohibited medication.

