8.3.4.2 Analysis of secondary efficacy endpoints: Part A

All secondary efficacy analyses will be analyzed with the ITT set.

The number of PRBC transfusions from Week 5 to Week 24 in each treatment group will be compared using a negative binomial regression model. The model-based estimate of the treatment effect and corresponding 95 % CI and p-value will be calculated. Patients who withdraw from treatment or receive prohibited medication before Week 24 will have the number of transfusions estimated from the duration that they were in the study until withdrawal or initiation of prohibited medication.

The change from Baseline at Week 24 in LDH, haptoglobin, indirect bilirubin, ARC and D-dimer will be analyzed using MMRM analysis with the fixed effects of treatment, strata, visit, visit-by-treatment interaction, and the respective Baseline level as covariate, using an unstructured covariance matrix and the Kenward-Roger method for calculating the degrees of freedom. Should the model fail to converge with an unstructured covariance matrix, other covariance structures will be explored. Details will be described in the SAP. The difference between treatment groups will be estimated, along with its 95 % CI and p-value. All data after the ICEs (as described in Section 8.3.4.1) will be set to missing, and the strategy for handling ICEs will be the same as that for the analysis of change from Baseline to Week 24 in Hb, as described in Section 8.3.4.1.

For the endpoint regarding the normalization of markers of hemolysis (LDH, indirect bilirubin and ARC), at Week 24, the number and percentage of patients who respond will be tabulated by treatment group and compared between treatment groups using an exact CMH test stratified for the strata ($\geq 1 / 0$ transfusions during the 6-month period prior to randomization). The strategy for handling ICEs will be the same as for the primary endpoint where patients meeting an ICE will be considered not normalized.

Kaplan-Meier plots will be presented for the time-to-event endpoints of time to normalization from Baseline to Week 24 for LDH, Hb, indirect bilirubin and ARC for each treatment group at Week 24, and survival estimates will be provided.

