The number of units of PRBCs transfused from Week 5 to Week 24 in each treatment group will be compared using a Wilcoxon rank-sum test. The difference between the medians will be estimated along with its 95 % CI. Patients who withdraw from treatment or study or receive prohibited medication before Week 24 will have the number of units estimated from the duration that they were in the study until withdrawal or initiation of prohibited medication.

The change from Baseline at Week 24 in FACIT-F, SF-12 and EQ-5D-5L will be analyzed using MMRM with the fixed effects of treatment, strata, visit, visit-by-treatment interaction and the respective Baseline level as covariate, using an unstructured covariance matrix and the Kenward-Roger method for calculating the degrees of freedom. Should the model fail to converge with an unstructured covariance matrix other covariance structures will be explored. Details will be described in the SAP. The difference between treatment groups will be estimated, along with its 95 % CI and p-value. All data after the ICEs (as described in Section 8.3.4.1) will be set to missing, and the strategy for handling ICEs will be the same as that for the analysis of change from Baseline to Week 24 in Hb, as described in Section 8.3.4.1.

Summary statistics by treatment groups will be presented at each assessment visit during the 24-week double-blind treatment period.

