## 7 STUDY ENDPOINT ANALYSES

### 7.1 PRIMARY ENDPOINT ANALYSIS

The primary endpoint is response to treatment at Week 24, with response defined as:

- An increase in Hb of  $\geq 1.5$  g/dL from Baseline or Hb normalization at Week 16; AND
- Maintenance of this effect from Week 16 to Week 24; AND
- The absence of PRBC transfusions (between Week 5 and Week 24)

Note: Hb normalization is defined as within normal range ( $\leq$  the ULN and  $\geq$  the LLN, as set by the testing laboratory reference ranges. Hb will be assessed locally.

Maintenance of effect is defined as the average change from Baseline in Hb of Week 16, Week 20 and Week 24  $\geq 1.5$  g/dL or the average Hb at these time points within normal range.

If response can't be evaluated (Hb at Week 16 and/or at Week 24 is missing) the patient will be considered to be a non-responder. If data at Week 20 is missing, the average of Week 16 and Week 24 will be used to calculate maintenance of effect.

The absence of PRBC transfusions will be assessed from Day 29 and until the end of the double-blind period (Week 24 or early withdrawal).

The primary analysis will be conducted on the ITT.

The estimand will be a composite where patients having an ICE will be considered as non-responders. The ICES of interest are:

- Withdrawal from treatment or lost to follow-up before end of the double-blind period
- Use of prohibited medications (rituximab alone or in combination, any other complement inhibitor, any other investigational drug and plasma exchange. ).

The number and percentage of patients who respond will be tabulated by treatment group and compared between treatment groups using an exact Cochran-Mantel-Haenszel (CMH) test stratified for the criterion used for stratification of randomization ( $\geq 1/0$  transfusions during the 6-month period prior to randomization). The odds ratio of being a responder for the pegcetacoplan treatment group versus the placebo group and associated exact 95% CI and p-

value will be provided. The responder rate, difference between treatment groups and 95% CI will also be reported.

As supportive analyses, the above will be repeated using the PP set and mITT set.

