### **7.2.3 Transfusion avoidance (Yes/No) from Week 5 to Week 24**

Transfusion avoidance (Yes/No) from Week 5 to Week 24 (Day 29 until end of double-blind period, which is Week 24 or early withdrawal) will be tabulated by treatment group and compared between treatment groups using an exact CMH test stratified for the criterion used for randomization stratification ( $\geq 1/0$  transfusions during the 6-month period prior to randomization). The odds ratio of showing transfusion avoidance from Week 5 to Week 24 for the pegcetacoplan treatment group versus the placebo group and associated 95% CI will be provided.

The composite strategy will be used as the estimand where patients meeting any of the ICEs will be considered as non-responders (transfusion avoidance=No).

- Withdrawal from treatment or lost to follow-up before end of the double-blind period.
- Use of prohibited medications (rituximab alone or in combination, any other complement inhibitor, any other investigational drug and plasma exchange. Phlebotomy/venesection is not included) during the double-blind period.
- Transfusion from week 5 to week 24 (Day 29 until end of double-blind period).

Transfusions before Week 5 (Day 29) are not counted and not considered an ICE but patients who withdraw or use prohibited medication before Week 5 will be considered non-responders (transfusion avoidance=No).

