### **7.3.4 Number of units of PRBCs transfused from Week 5 to Week 24**

The number of units of PRBCs transfused from Week 5 to Week 24 in each treatment group will be compared using a stratified Wilcoxon rank-sum test (i.e., the Van Elteren test). Patients who withdraw before Week 24 will have the number of units estimated from the duration that they were in the study until withdrawal or initiation of prohibited medication.

The average number of units transfused for the duration where a patient has evaluable data for PRBC transfusions will be used to estimate the total number of transfused units that would have been used through Week 24 had they not withdrawn from the study.

If the number of PRBC is reported in units and mL in the database the mL will be converted to units using the following formula:

$$\text{Number of PRBC units} = \text{Round}(\text{PRBC (mL)} / 300), 1.$$

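### SAP 7.3.1 and 7.3.4 drop the protocol's between-group estimates and 95% CIs for transfusion number and units; the projection for early stoppers also lacks a start day

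*SAP*

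**What the plan says.** **Number of transfusions.** Protocol 8.3.4.2 compares the groups by negative binomial regression and adds: "The model-based estimate of the treatment effect and corresponding 95 % CI and p-value will be calculated". In SAP 7.3.1 the groups are "compared using a stratified Wilcoxon rank-sum test-p-value will be calculated. Crude rates of transfusions will be calculated for the double-blind period (Part A". No contrast between arms and no CI is named.

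**Units transfused.** Protocol 8.3.4.2 plans a rank-sum test and states: "The difference between the medians will be estimated along with its 95 % CI". SAP 7.3.4 keeps a stratified rank test (van Elteren) and leaves the estimate and its interval out.

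**Early stoppers.** For patients who come off treatment early or start a prohibited drug, the protocol's rule is that they "will have the number of transfusions estimated from the duration that they were in the study until withdrawal or initiation of prohibited medication". SAP 7.3.1 repeats this rule. For units, SAP 7.3.4 uses the average over the evaluable duration to "estimate the total number of transfused units that would have been used through Week 24 had they not withdrawn from the study". None of these texts gives the day on which the duration starts.

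**The window elsewhere in the SAP.** Section 7.1: "The absence of PRBC transfusions will be assessed from Day 29 and until the end of the double-blind period (Week 24 or early withdrawal". Section 7.2.3: "Transfusions before Week 5 (Day 29) are not counted and not considered an ICE". For early stops, 7.2.3 adds that "patients who withdraw or use prohibited medication before Week 5 will be considered non-responders (transfusion avoidance=No".

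**Status.** SAP 11.1 gives the SAP precedence over the protocol and lists no changes. SAP 1.1 keeps the Part A primary and secondary efficacy analyses and drops supportive and sensitivity analyses.

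**The concern.** Protocol 5.2 makes the effect on the number of PRBC transfusions a key secondary objective. A rank-test p-value says whether the arms differ in order, not by how much. Crude rates by arm give a descriptive idea of size but no interval for the difference. Transfusion avoidance has an odds ratio with CI, but it is a yes/no outcome and cannot show how many transfusions were prevented. In a trial whose enrolment stopped early, an interval is the most useful output for a count, because it shows which effects the data can and cannot exclude.

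The second issue is reproducibility. SAP 10.2 relies on two programmers working independently from the specifications. With no start day for the projection, and no rule for a patient who stops before Day 29, they could derive different values.

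**Working it through.** **1. Outputs side by side**

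| Endpoint | Protocol 8.3.4.2 | SAP |
|---|---|---|
| Number of transfusions | Negative binomial effect, 95% CI, p-value | 7.3.1: stratified rank-test p-value, crude rates |
| Units | Rank-sum test, difference in medians, 95% CI | 7.3.4: stratified rank test |

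The estimate and interval are missing from both SAP rows. SAP 1.1 does not remove them, since neither is a supportive or sensitivity analysis. The plan gives no sizing figure for these endpoints to reproduce; the 54 and 57 patients belong to the primary endpoint.

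**2. Start day for one patient**

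With a Day 29 start, the window is Days 29-168, which is 168 - 28 = 140 days. For k in-window transfusions and a stop on Day t:
- Day 29 denominator: k x 140/(t - 28)
- Day 1 denominator: k x 140/t
- Ratio of the two: t/(t - 28)

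For k = 1 (stop days are illustrative):

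| Stop day | From Day 29 | From Day 1 | Ratio |
|---|---|---|---|
| 42 | 140/14 = 10.0 | 140/42 = 3.3 | 3.00 |
| 57 | 140/29 = 4.8 | 140/57 = 2.5 | 1.97 |
| 85 | 140/57 = 2.5 | 140/85 = 1.6 | 1.49 |
| 141 | 140/113 = 1.2 | 140/141 = 1.0 | 1.25 |

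For a stop before Day 29, the Day 29 denominator does not exist.

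**3. Effect on the test**

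All inputs are assumed: placebo mean 1 or 3 transfusions per 140 days, stratum means 0.5 and 1.5 times that, gamma dispersion 1, 10% per arm stopping on Days 7-70, and arms of 38/19 (57 split 2:1) or an assumed truncated 16/8. Share of simulated trials in which the two readings give different verdicts at 5%:
- Same in-window counts, only the denominator differs, pre-Day-29 stoppers left out of both: about 0.2-1.5%.
- The same, but pre-Day-29 stoppers kept as zero under the Day 1 reading: about 3-6% at a true rate ratio of 0.4.
- Transfusions before Day 29 also counted: about 6-13% at a true ratio of 0.4.

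**4. Is a rule for an arm with no transfusions needed?**

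Protocol 4.1.2.1 reports 77% transfusion avoidance over 12 months in the phase 2 CAD cohort. Solving P(0) = 0.77 without overdispersion gives -ln(0.77) = 0.26 per year, or 0.26 x 140/365 = 0.100 per window. The chance that nobody in the active arm is transfused is then exp(-38 x 0.100) = 2.2% with 38 patients and exp(-16 x 0.100) = 20.1% with 16. With dispersion 1 or 2 the window mean is 0.115 or 0.132, and the chances are 1.6% or 1.2% (38 patients) and 17.6% or 15.4% (16 patients). A zero arm is therefore realistic in a truncated trial.

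**5. Behaviour of a plain Wald CI**

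With placebo means of 1-3, ratios of 1 and 0.4, and dispersion 1-2, simulated coverage was 91.7-95.0% at 38/19 and 89.3-95.7% at 16/8. At a ratio of 0.4 the active means are 0.4-1.2, which is 3 to 12 times the phase 2 figures in step 4 (0.4/0.132 = 3; 1.2/0.100 = 12). These coverages are therefore only a guide, and no CI width is predicted here.

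**The case against.** **Start day.** A reader might infer from the third line of step 3 that the missing start day puts the result at real risk. The documents do not support that. The endpoint is named Week 5 to Week 24, and SAP 7.2.3 reads the same phrase as Day 29 onward and excludes earlier transfusions. Counting a transfusion before Day 29 would contradict the endpoint's own name. What remains open is the denominator and the handling of stops before Day 29, and the effect of those is small. The gap is also inherited from the protocol, so it is not a departure by the SAP.

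**Crude rates.** A reader might infer that they cover all 24 weeks, including 28 of 168 days (17%) outside the window. The mention of Part A may only separate it from Parts B and C. The wording is unclear rather than wrong.

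**Disclosure.** Protocol section 8 says deviations from the protocol will be discussed in the clinical study report, so a route exists. It would disclose the omission but would not produce an estimate.

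**Importance.** SAP 7.2 limits the hierarchy to the primary and key secondary endpoints, so it is also wrong to infer that type I error control is at stake. This objection stands, and it keeps the point modest.

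None of this answers the main point: neither SAP section names an effect estimate or interval.

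**Conclusion.** The point holds as a cheap improvement. Followed as written, the SAP will produce no between-group effect size or CI for the number of transfusions or for units, although the protocol planned both and a key secondary objective concerns the number. This rests on the text alone and is firm. Early termination does not explain it.

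The start-day gap is a clarification. Its size, about 0.2-1.5% changed verdicts from the denominator alone and about 3-6% at a true ratio of 0.4 if pre-Day-29 stoppers are kept as zero, depends on the assumed transfusion rates, dispersion, stopping pattern and arm sizes. The documents give no transfusion rates or dispersion for this trial.

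**What to change.** **SAP 7.3.1**
- Keep the stratified rank test for the p-value.
- Add the protocol's negative binomial rate ratio with 95% CI. Fit it to observed, unprojected counts from Day 29, with treatment, stratum and offset log(days from Day 29 to the earliest of withdrawal, prohibited medication or end of Part A).
- If an arm has no transfusions or the fit fails, report each arm's crude rate with an exact CI.

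**SAP 7.3.1 and 7.3.4**
- State Day 29 as the start for the projection and for the crude rates.
- Say that patients with no days in the window contribute no exposure.

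**SAP 7.3.4**
- Restore the difference in medians with 95% CI, or state why it is dropped and show the distribution of units by arm. The second option may be more informative. With counts standing in for units (38/19, ratio 0.4, 10% stopping per arm), both medians were 0 in 76-89% of simulated trials at a placebo mean of 1 and in 4-29% at a mean of 3.

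**SAP 11.1**
- Record these changes.

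**Cost.** SAP wording and one additional model, with no new data. In the truncated trial the CI will be wide and may be too narrow for its nominal level. It can disagree with the rank-test p-value. The model assumes that stopping is unrelated to transfusion need, as the projection already does. An early stopper with no transfusions still ties for the best rank, and this change does not cure that. An exact Poisson CI in the fallback ignores overdispersion.

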#### **7.3.2 Change from Baseline at Week 24 in LDH, haptoglobin, indirect bilirubin, ARC and D-dimer**

The change from Baseline at Week 24 in LDH, haptoglobin, indirect bilirubin, ARC and D-dimer will be analyzed using MMRM analysis with the fixed effects of treatment, strata, visit, visit-by-treatment interaction, and the respective Baseline level as covariate, using an unstructured covariance matrix and the Kenward-Roger method for calculating the degrees of freedom. Should the model fail to converge with an unstructured covariance matrix, other covariance structures may be explored (unstructured will be attempted first, followed by compound symmetry, followed by AR(1), if needed). The difference between treatment groups will be estimated, along with its 95% CI and p-value

The ICEs and their associated strategies to handle data following the ICEs, will be the same as for the key secondary endpoint Change from Baseline to Week 24 in Hb level in section 7.2.1. Additional (descriptive only) summary tables of change from baseline irrespective of ICEs will be

created for LDH, Haptoglobin, ARC, and indirect bilirubin. No MMRM modeling will be included.

Central laboratory values will be used for the endpoint assessments above except ARC which will be assessed locally.

### **7.3.3 Normalization of markers of hemolysis (LDH, indirect bilirubin and ARC) at Week 24**

For the normalization of markers of hemolysis (LDH, indirect bilirubin and ARC) at Week 24, the number and percentage of patients who achieve normalization will be tabulated by treatment group and compared between treatment groups using an exact CMH test stratified for the criterion used for randomization strata ( $\geq 1/0$  transfusions during the 6-month period prior to randomization). The strategy for handling ICEs will be the same as for the primary endpoint where patients meeting an ICE will be considered not normalized. A parameter is considered to have met the normalization response criteria if the patient has a non-normal result at baseline and then has a lab value for that parameter which is in the normal range post-baseline, as defined in the laboratory data.

If data at Week 24 is missing the patient will be considered not normalized.

A composite strategy for handling of ICEs will be used for these endpoints, if any of the ICEs as listed below occurs, the patient is not considered normalized at Week 24 and will be set to non-responder.

- Withdrawal from treatment or lost to follow-up before end of the double-blind period
- Use of prohibited medications (rituximab alone or in combination, any other complement inhibitor, any other investigational drug and plasma exchange. Phlebotomy/venesection is not included).
- Transfusion from Week 5 to Week 24.

Kaplan-Meier plots will be presented for the time-to-event endpoints of time to first normalization from Baseline to Week 24 for LDH, Hb, indirect bilirubin and ARC for each treatment group at Week 24, and Kaplan-Meier estimates will be provided.

Central laboratory values will be used for the endpoint assessments above except ARC which will be assessed locally.

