6.3 Selection of study population

6.3.1 Inclusion criteria

A patient must fulfill the following criteria to be included in the study:

1. Age 18 years or older.
2. Diagnosis of primary CAD on the basis of the presence of all the following criteria at screening:
 - a. Signs of hemolysis with abnormal values for at least 2 of the following hemolytic markers:
 - i. Reduced haptoglobin level (< LLN).
 - ii. Elevated LDH level (> ULN).
 - iii. Elevated indirect bilirubin level (> ULN; > 3 x ULN for patients with Gilbert-Meilengracht syndrome).

iv. Increased ARC (above the ULN).

- b. Monospecific direct antiglobulin test strongly positive for C3d.
- c. Cold agglutinin titer ≥ 64 at 4°C .

3. Hb level ≤ 9 g/dL at screening.
4. An absolute neutrophil count ≥ 1500 cells/mm 3 at screening.
5. Documented results from bone marrow biopsy within 1 year of screening with lymphoproliferative infiltration $\leq 20\%$. Patients who have not received a bone marrow biopsy within 1 year of their screening visit or for whom bone marrow biopsy reports are incomplete or unavailable will be required to receive a bone marrow biopsy to determine eligibility.
6. Body weight ≤ 100 kg.
7. Either have vaccination against *S. pneumoniae*, *N. meningitidis* (Types A, C, W, Y, and B), and *H. influenzae* (Type B) within 2 years prior to screening or agree to receive vaccination during screening as follows:
 - First dose of vaccine against *N. meningitidis* Types A, C, W, and Y at least 2 weeks prior to start of study drug with second dose 2 months later (Study Day 57), and then boosters every 5 years.
 - First dose of the vaccine against *N. meningitidis* Type B at least 2 weeks prior to start of study drug with a second dose after at least 1 month (Study Day 29). First booster dose 1 year later, and then additional booster doses every 2 to 3 years.
 - *S. pneumoniae*: PCV13 and/or PPSV23 as per ACIP guidelines for adults or children with immunocompromising conditions.
 - *H. influenzae* Type B: 1 dose at least 2 weeks prior to start of study drug.

Vaccination is mandatory unless documented evidence exists that patients are nonresponders to vaccination. Vaccinations should be administered following the ACIP recommendations for adults or children with complement deficiencies and/or immunocompromising conditions.

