### **4.3 INTENT-TO-TREAT SET**

The intent-to-treat (ITT) set will include all randomized patients. Patients will be analyzed according to their assigned treatment, regardless of the treatment actually received. The ITT set will be used for all efficacy analysis.

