### **5 GENERAL ASPECTS FOR STATISTICAL ANALYSES**

#### **5.1 GENERAL METHODS**

- All analyses and summaries will be produced using SAS® version 9.4 (or higher).
- Categorical variables will be summarized using the number of observations (n), frequency and percentage of patients. All percentages will be presented as 1-decimal point, unless otherwise specified. Percentages equal to 100 will be presented as 100 % and percentages will not be presented for zero frequencies.
- Continuous variables and ordered categorical data will be summarized using the number of patients with evaluable data, mean, standard deviation (SD), geometric mean (where appropriate), median, first and third quartiles, minimum and maximum. The same precision as in the raw data will be presented when reporting minimum and maximum, 1 more decimal place than in the raw data will be presented when reporting the mean and median, and 2 more decimal places than in the raw data will be presented when reporting the SD. For ordered categorical data and nominal data, absolute counts and relative frequencies (in %) will be calculated.
- Lower and upper bound values for the CIs will be reported to 2 more decimal places than the raw data.
- All statistical hypothesis tests and confidence intervals will be 2-sided, using a type I error rate of 0.050.
- Unless stated otherwise, the percentages will be based on the number of non-missing observations. The column header will still contain the number of patients in the treatment group. There will be a row for the number of non-missing observations in the table (at each time point, if required) for each variable being summarized.
- Any calculated p-values will be presented to 3 decimal places; p-values less than 0.001 will be presented as ‘p<0.001’ and p-values greater than 0.999 will be presented as ‘p>0.999’.
- All collected patient data and relevant summaries and derivations will be included in listings and sorted by treatment group, Subject ID, and visit, as applicable, for all randomized patients.

- All TLFs will include footers that identify the name of the program that created the output, together with the date and time on which it was created. Headers will include the total number of pages that the presentation contains and, for each page, the number of the page within the presentation.

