##### 9.2.5.2 *Table conventions*

- Units will be included where available
- If the categories of a parameter are ordered, then all categories between the maximum and minimum category should be presented in the table, even if n=0 for all treatment groups in a given category that is between the minimum and maximum level for that parameter. For example, the frequency distribution for symptom severity would appear as:

Severity Rating	N
very severe	2
severe	0
moderate	8
mild	3

Where percentages are presented in these tables, zero percentages will not be presented and so any counts of 0 will be presented as 0 and not as 0 (0%).

- If the categories are not ordered (e.g., Medical History, Reasons for Discontinuation from the Study, etc.), then only those categories for which there is at least 1 patient represented in 1 or more groups should be included.
- An Unknown or Missing category should be added to any parameter for which information is not available for 1 or more patients.
- Unless otherwise specified, the estimated mean and median for a set of values should be presented to 1 more significant digit than the original values, and standard deviations should be presented to 2 more significant digits than the original values. The minimum and maximum

should report the same significant digits as the original values. For example, for systolic blood pressure:

N	XX
Mean	XXX.X
Std Dev	X.XX
Median	XXX.X
Minimum	XXX
Maximum	XXX

- P-values should be output in the format: “0.xxx”, where xxx is the value rounded to 3 decimal places. Any p-value less than 0.001 will be presented as < 0.001. If the p-value should be less than 0.0001 then present as < 0.0001. If the p-value is returned as > 0.999 then present as > 0.999
- Percentage values should be printed to 1 decimal place, in parentheses with no spaces, 1 space after the count (e.g., 7 [12.8%], 13 [5.4%]). Values that round down to 0.0 will be displayed as ‘< 0.1’. Unless otherwise noted, for all percentages, the number of patients in the analysis set for the treatment group who have an observation will be the denominator. Percentages after zero counts should not be displayed and percentages equating to 100 % should be presented as 100 %.

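### SAP 7.3.3 requires a non-normal baseline for marker normalization but sets no matching denominator, so baseline-normal patients are counted and cannot succeed

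*SAP*

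**What the plan says.** **Numerator.** SAP 7.3.3 treats a marker as normalized when "the patient has a non-normal result at baseline and then has a lab value for that parameter which is in the normal range post-baseline". The comparison is an exact CMH test stratified by transfusion history. Patients with an intercurrent event count as failures, and so do those without a Week 24 value: "If data at Week 24 is missing the patient will be considered not normalized".

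**Analysis set.** SAP 7.3 states that "All secondary efficacy analyses will be analyzed with the ITT set", and SAP 4.3 that "The ITT set will be used for all efficacy analysis". ITT means everyone randomized.

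**Denominator.** SAP 7.3.3 gives none. The general rule in SAP 5.1 is "Unless stated otherwise, the percentages will be based on the number of non-missing observations". The table rule in SAP 9.2.5.2 is similar, unless noted otherwise: "for all percentages, the number of patients in the analysis set for the treatment group who have an observation will be the denominator". The same section adds that choosing a denominator can need care and leaves details to table footnotes. It gives no rule for normalization.

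**Eligibility.** Protocol 6.3.1 asks for "Signs of hemolysis with abnormal values for at least 2 of the following hemolytic markers", listing haptoglobin, LDH, indirect bilirubin and ARC.

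**Time to event.** SAP 7.3.3 also plans Kaplan-Meier plots of "time to first normalization from Baseline to Week 24 for LDH, Hb, indirect bilirubin and ARC". It does not say what counts as an event or who is at risk.

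**Protocol.** Section 8.3.4.2 of the Protocol describes the Week 24 normalization analysis without an abnormal-baseline condition.

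**After early termination.** SAP 1.1 keeps the Part A secondary endpoints, drops normalization beyond Part A and cancels sensitivity analyses.

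**The concern.** The numerator is limited to patients who start abnormal, while the denominator, read literally, is everyone randomized. A patient whose LDH is normal at baseline and stays normal is scored as a treatment failure for LDH.

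The reported percentage then mixes two things: how often the drug corrects an abnormal marker, and how many patients had an abnormal marker to correct. The second is case mix, fixed before dosing. It pulls both arms' rates and their difference toward zero, by a different amount for each marker, so the three markers cannot be compared with each other or with other studies. Since Part A is now the only place where these endpoints are reported, no later table would expose the problem.

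**Working it through.** **1. The plan's own figure.** The only sizing figure is for the primary endpoint (Protocol 8.1, SAP 2.3): 54 patients at 55% vs 10%. Exact enumeration of the two-sided Fisher test gives 89.8% power at 34/17 and 92.5% at 36/18, so 54 is reproduced as the smallest 2:1 total reaching 90%. With the 5% allowance, 54/0.95 = 56.8, hence 57 (38/19). Nothing is sized for normalization.

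**2. Can baseline-normal patients enter?** Yes. Low haptoglobin plus one other abnormal marker satisfies the entry rule and leaves two of the three endpoint markers free to be normal. The rule is applied at screening, whereas baseline is the last pre-dose value (SAP 5.2.1), so a marker abnormal at screening may also be normal at baseline.

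**3. Effect on the estimate.** Let f be the baseline-normal share, equal in both arms, and p₁ and p₀ the normalization rates among baseline-abnormal patients.

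- Full ITT rates: p₁(1 − f) and p₀(1 − f).
- Full ITT difference: (p₁ − p₀)(1 − f).

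The factor (1 − f) holds for any rates. With assumed p₁ = 60%, p₀ = 20%, f = 30%: 0.6 × 0.7 = 42%, 0.2 × 0.7 = 14%, difference 28 points instead of 40.

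**4. Chance imbalance in f.** At the same rates:

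- f of 20% (active) and 40% (placebo): 0.6 × 0.8 − 0.2 × 0.6 = 36 points.
- f of 40% and 20%: 0.6 × 0.6 − 0.2 × 0.8 = 20 points.

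Against 28 when balanced, this spread has nothing to do with treatment.

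**5. Power.** Two-sided Fisher test at 5%, full enumeration. The full ITT column uses the diluted rates on everyone. The restricted column uses the undiluted rates, with at-risk counts Binomial(n, 1 − f) in each arm. The 24/12 size is an assumption, because the documents do not give the final enrolment.

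| Assumed rates | f | 38/19: full ITT vs restricted | 24/12: full ITT vs restricted |
|---|---|---|---|
| 60% vs 20% | 5% | 77.5% vs 80.1% | 54.1% vs 53.2% |
| 60% vs 20% | 30% | 53.8% vs 62.6% | 32.4% vs 39.0% |
| 40% vs 10% | 30% | 42.6% vs 43.0% | 16.6% vs 19.3% |
| 30% vs 5% | 30% | 34.1% vs 33.2% | 7.5% vs 9.0% |

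Simulating the planned stratified exact CMH test (40,000 trials, two near-equal strata, same rates in each) agrees at 60% vs 20%, f = 30%: 54.1% vs 62.3% at 38/19, and 32.5% vs 38.4% at 24/12.

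**6. Type I error.** CMH simulation at 38/19, f = 30%, 30% normalizing in both arms: 3.75% on full ITT and 3.24% restricted, both below 5%.

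**7. Time to first normalization.** If the abnormal-baseline condition also defines the event and all ITT patients are at risk, baseline-normal patients can never have an event and the curves cannot exceed 1 − f (70% at f = 30%).

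**The case against.** **The denominator is open, not wrong.** Both defaults can be overridden, SAP 9.2.5.2 allows a footnoted denominator, and table specifications follow the SAP (SAP 10.1). A programmer could set baseline-normal patients to missing. This stands as a possibility, but none of it is prespecified. Followed as written, the text keeps these patients in as failures.

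**Full-ITT failure counting is conventional.** It fits the composite rule for missing data and intercurrent events, and the expected distortion is toward no effect. That is true. But those rules deal with what happens after randomization; a normal baseline value is known before dosing and says nothing about treatment failure.

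**The size is unknown.** This stands. Two of four markers is an eligibility floor, not evidence of how many patients are normal on any marker. If everyone is abnormal at baseline on a marker, there is no dilution for it.

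**Stronger readings a reader might infer.**

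- *The rule always costs power.* Not supported: at 38/19 and f = 30%, restriction gains nothing at 40% vs 10% and loses slightly at 30% vs 5%.
- *The Kaplan-Meier curves are capped.* Not established: the SAP gives no event rule for them.
- *The SAP contradicts the Protocol.* Weak: normalization ordinarily implies a change from abnormal, and SAP 11.1 gives the SAP precedence. The fault is that the condition came without a denominator.

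**Conclusion.** The concern holds in this form: SAP 7.3.3 ties success to a non-normal baseline and leaves the denominator to defaults that retain patients who cannot succeed. The multiplication of each rate and of the difference by (1 − f) is arithmetic, given equal f in both arms. Its size rests on f and on marker-specific rates, neither of which is in the documents; 28 instead of 40 points is one illustration.

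The certain harm is to the meaning of the reported rates and differences. The power effect is secondary and depends on rates, share and sample size. At 24/12 and f = 30%, restriction helps in all three scenarios; at f = 5% the choice hardly matters.

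These are secondary endpoints outside the testing hierarchy. Type I error is not inflated, and the primary and key secondary conclusions do not change. The correction should be made, but it does not bear on whether the trial meets its main objectives.

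**What to change.** Add one sentence to SAP 7.3.3: for each of LDH, indirect bilirubin and ARC, the Week 24 normalization table, the exact CMH test and the Part A time-to-first-normalization curve include only ITT patients with a non-normal Baseline value for that marker. Report the baseline-normal count per arm beside each result, and state the event rule for the curves. If the blind has already been broken, label the restricted analysis post hoc.

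The cost is one filter on a pre-dose value. The downside is smaller denominators that differ by marker, and power may not improve.

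Counting every ITT patient in range at Week 24, whatever the baseline, would also be coherent and closer to Protocol 8.3.4.2, but it does not restore the difference. At 60% vs 20% and f = 30%, with an assumed 90% of baseline-normal patients staying in range in both arms, the rates are 0.6 × 0.7 + 0.9 × 0.3 = 69% and 0.2 × 0.7 + 0.9 × 0.3 = 41%. That is again 28 points, with Fisher power of 48% at 38/19.
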